6.4 Categorical Analysis

Results for categorical outliers will be summarized in frequency tables with counts and percentages for both number of subjects and number of time points. Subject data will be summarized using the count of distinct subjects that fall into the category and the percentage of the total number of subjects. Time point data will be summarized using the count of time points at which the assessments fall into the category and the percentage of the total number of time

points at which assessments are performed. Counts (either number of subjects or number of time points) for each treatment group will be used as the denominator in the calculation of percentages unless otherwise specified.

A subject or time point will be determined as an outlier if the following criteria (which are assessed separately) are met for the ECG intervals ([Table 5](#)).

Table 5 Criteria for determining a subject or time point outlier

ECG interval	Categorical outlier criteria
QTcF	Treatment-emergent value of > 450 and ≤ 480 ms when not present at baseline (new onset)
	Treatment-emergent value of > 480 and ≤ 500 ms when not present at baseline (new onset)
	Treatment-emergent value of > 500 ms when not present at baseline (new onset)
	Increase of QTc from baseline of > 30 and ≤ 60 ms
	Increase of QTc from baseline > 60 ms
PR	Increase of PR from baseline $> 25\%$ resulting in PR > 200 ms
QRS	Increase of QRS from baseline $> 25\%$ resulting in QRS > 120 ms
HR	Decrease of HR from baseline $> 25\%$ resulting in HR < 50 bpm
	Increase of HR from baseline $> 25\%$ resulting in HR > 100 bpm

All outliers will be summarized for each treatment on the basis of incidence rates. A subject will be counted only once for a particular outlier event if the subject experiences more than 1 episode of that event. The total number of time points will be based on the number of observed time points across all subjects within a treatment group.

6.5 Morphological analysis for T-wave and U-wave

Morphological analyses will be performed with a focus on detecting changes in T-wave morphology and appearance of abnormal U-waves. The analyses will evaluate change-from-baseline (i.e., treatment-emergent changes). For each category of T-wave morphology and of U waves, the category will be deemed as present if observed in any replicates at the time point. For baseline, the category will be deemed as present if observed in any replicates from all time points that constitute baseline.

The analysis results for T-wave morphology and U-wave presence will be summarized in frequency tables with counts and percentages for both number of subjects and number of time points. The number and percentage of subjects in each treatment group having changes from baseline that represent the appearance of the morphological abnormality will be also summarized. The total number of time points having a particular change event will be summarized in terms of number and percentage based on the number of observed time points across all subjects within a treatment group.

6.6 Determination of Sample Size

Approximately 68 healthy subjects (at least 30% for each sex) will be randomized into 2 groups (Group 1 and 2) with 34 subjects in each. Group 2 consists of 2 sub-groups (Group 2A and 2B) and each sub-group will be randomized with 17 subjects.

Determination of sample size for primary analysis

A sample size of 28 evaluable subjects per treatment group will provide more than 94.4% power to exclude that CBP-307 causes more than 10-ms QTc effect at clinically relevant plasma levels, as shown by the upper bound of the 2-sided 90% confidence interval (CI) of the model-predicted QT effect ($\Delta\Delta\text{QTcF}$) at the observed geometric mean C_{max} of CBP-307 in the study. This power is estimated approximately using a 2-sample t-test. The calculation assumes a 1-sided 5% significance level, an underlying effect of CBP-307 of 3 ms and a standard deviation (SD) of the ΔQTcF of 8 ms for both CBP-307 and placebo treatment groups. Note that this calculation is conservative, since it does not take into account any gain in precision due to the use of all data of each subject with the help of a linear mixed-effects model. The concentration-QTc analysis method is supported by Darpo et al⁵ and Ferber et al⁶, and consistent with the experiences from 25 recent TQT studies.

Determination of sample size for assay sensitivity analysis

To demonstrate assay sensitivity with concentration-QTc analysis, it has to be shown that the $\Delta\Delta\text{QTcF}$ of a single dose of 400 mg moxifloxacin exceeds 5 ms (i.e., the lower bound of the 2-sided 90% CI of the predicted QTc effect [$\Delta\Delta\text{QTcF}$] should exceed 5 ms). In a similarly designed, recent crossover study with 24 healthy subjects (on-file data, ERT), the standard error (SE) for the prediction of the QT effect of moxifloxacin based on the exposure-response analysis was 1.24 ms. The within-subject SD of ΔQTcF in the referred study was 5.4 ms based on the by-time point analysis. If the effect of moxifloxacin is assumed to be 10 ms, the SE of 1.24 ms corresponds to an effect size of $(10-5)/(1.24 \times \sqrt{24}) = 0.82$, where the effect size is the effect assumed under the alternative hypothesis divided by the SD of the test variable. This value should be compared to the effect size of 0.64 required to guarantee a power of at least 95% in a paired t-test situation with a sample size of 28 evaluable subjects. In other words, based on this calculation, a power of at least 95% will be obtained as long as the variability of the ΔQTcF , as measured by its within-subject SD from the by-time point analysis, does not exceed 6.9 ms (ie, 128% [$= 0.82/0.64$] of the 5.4 ms observed in the referred study assuming the ratio of effective sizes is consistent with inverse ratio of within-subject SD). The number also agrees with recent recommendations of the FDA, which propose at least 20 subjects (Huang et al⁷).

7 References

3. Cleveland WS. Robust locally weighted regression and smoothing scatterplots. *J Am Stat Assoc*. 1979;74(368):829-836.

8.1 Tables

Number	Title	Comments
14.1.1.1	Baseline values of ECG parameters with descriptive statistics for CBP-307 analysis	n, mean, SD, 90% CI, median, minimum, and maximum from descriptive summary will be given by treatment for each ECG parameter (Section 5.3).
14.1.1.2	Baseline values of ECG parameters with descriptive statistics for moxifloxacin analysis	n, mean, SD, 90% CI, median, minimum, and maximum from descriptive summary will be given by treatment for each ECG parameter (Section 5.3).
14.1.2.1	Observed values of QTcF with descriptive statistics for CBP-307 analysis	n, mean, SD, 90% CI, median, minimum, and maximum from descriptive statistics will be given by treatment and post-baseline time point (Section 6.3).
14.1.2.2	Observed values of QTcF with descriptive statistics for moxifloxacin analysis	n, mean, SD, 90% CI, median, minimum, and maximum from descriptive statistics will be given by treatment and post-baseline time point (Section 6.3).

Number	Title	Comments
14.1.3.1- 14.1.3.4	Change-from-baseline QTcF, HR, PR, and QRS (Δ QTcF, Δ HR, Δ PR, and Δ QRS) at each time point for CBP-307 analysis	n, LS mean, SE, and 90% CI from the statistical modeling will be given by treatment and time point (Section 6.3).
14.1.4.1- 14.1.4.4	Change-from-baseline QTcF, HR, PR, and QRS (Δ QTcF, Δ HR, Δ PR, and Δ QRS) at each time point for moxifloxacin analysis	n, LS mean, SE, and 90% CI from the statistical modeling will be given by treatment and time point (Section 6.33).
14.1.5.1- 14.1.5.4	Placebo-corrected change-from-baseline QTcF, HR, PR, and QRS ($\Delta\Delta$ QTcF, $\Delta\Delta$ HR, $\Delta\Delta$ PR, and $\Delta\Delta$ QRS) at each time point for CBP-307 analysis	LS mean, SE, and 90% CI from the statistical modeling will be given by treatment and time point (Section 6.33).
14.1.6.1- 14.1.6.4	Placebo-corrected change-from-baseline QTcF, HR, PR, and QRS ($\Delta\Delta$ QTcF, $\Delta\Delta$ HR, $\Delta\Delta$ PR, and $\Delta\Delta$ QRS) at each time point for moxifloxacin analysis	LS mean, SE, and 90% CI from the statistical modeling will be given by treatment and time point (Section 6.33).
14.1.7.1	QTcF outliers per absolute category for CBP-307 analysis	Number (%) of subjects and time points with QTcF > 450 and ≤ 480 ms, > 480 and ≤ 500 ms, or > 500 ms by treatment (Section 6.4).
14.1.7.2	QTcF outliers per absolute category for moxifloxacin analysis	Number (%) of subjects and time points with QTcF > 450 and ≤ 480 ms, > 480 and ≤ 500 ms, or > 500 ms by treatment (Section 6.44).
14.1.8.1	QTcF outliers per change-from-baseline category for CBP-307 analysis	Number (%) of subjects and time points with Δ QTcF > 30 and ≤ 60 ms, or > 60 ms by treatment (Section 6.4).
14.1.8.2	QTcF outliers per change-from-baseline category for moxifloxacin analysis	Number (%) of subjects and time points with Δ QTcF > 30 and ≤ 60 ms, or > 60 ms by treatment (Section 6.44).
14.1.9.1	Categorical analyses for HR, PR, and QRS for CBP-307 analysis	Number (%) of subjects and time points with Δ PR $> 25\%$ and PR > 200 ms at post-dose; Δ QRS $> 25\%$ and QRS > 120 ms at post-dose; HR decrease from baseline $> 25\%$ and HR < 50 bpm at post-dose; and HR increase from baseline $> 25\%$ and HR > 100 bpm at post-dose (Section 6.4).

Number	Title	Comments
14.1.9.2	Categorical analyses for HR, PR, and QRS for moxifloxacin analysis	Number (%) of subjects and time points with $\Delta PR > 25\%$ and $PR > 200$ ms at post-dose; $\Delta QRS > 25\%$ and $QRS > 120$ ms at post-dose; HR decrease from baseline $> 25\%$ and $HR < 50$ bpm at post-dose; and HR increase from baseline $> 25\%$ and $HR > 100$ bpm at post-dose (Section 6.4).
14.1.10.1	T-wave morphology and U-wave presence across treatment groups: treatment-emergent changes for CBP-307 analysis	Number (%) of subjects and time points falling into each of the T-wave and U-wave categories will be given by treatment (Section 6.5).
14.1.10.2	T-wave morphology and U-wave presence across treatment groups: treatment-emergent changes for moxifloxacin analysis	Number (%) of subjects and time points falling into each of the T-wave and U-wave categories will be given by treatment (Section 6.55).
14.1.11.1	Concentration-QTc analysis of CBP-307 and associated $\Delta QTcF$ prolongation	Fixed-effect estimations and corresponding P values will be given (Section 6.1).
14.1.11.2	Assay sensitivity analysis of moxifloxacin and associated $\Delta QTcF$ prolongation	Fixed effect estimations and corresponding P values will be given (Section 6.2).
14.1.12.1	Predicted $\Delta\Delta QTcF$ interval at geometric mean peak CBP-307 concentration	Section 6.1 . Referred to above as a “Concentration-QTc prediction table.”
14.1.12.2	Predicted $\Delta\Delta QTcF$ interval at geometric mean peak moxifloxacin concentration	Section 6.2 . Referred to above as a “Concentration-QTc prediction table.”

8.2 Figures

Number	Title	Comments
14.2.1.1	Observed QTcF across time points for CBP-307 analysis	Mean and 90% CI from descriptive summary will be given by treatment (Section 6.33).
14.2.1.2	Observed QTcF across time points for moxifloxacin analysis	Mean and 90% CI from descriptive summary will be given by treatment (Section 6.33).
14.2.2.1-14.2.2.4	Change-from-baseline QTcF, HR, PR, and QRS ($\Delta QTcF$, ΔHR , ΔPR , and ΔQRS) across time point for CBP-307 analysis	LS mean and 90% CI from the statistical modeling will be shown by treatment (Section 6.3).

Number	Title	Comments
14.2.3.1- 14.2.3.4	Change-from-baseline QTcF, HR, PR, and QRS (Δ QTcF, Δ HR, Δ PR, and Δ QRS) across time point for moxifloxacin analysis	LS mean and 90% CI from the statistical modeling will be shown by treatment (Section 6.3).
14.2.4.1- 14.2.4.4	Placebo-corrected change-from-baseline QTcF, HR, PR, and QRS ($\Delta\Delta$ QTcF, $\Delta\Delta$ HR, $\Delta\Delta$ PR, and $\Delta\Delta$ QRS) across time point for CBP-307 analysis	LS mean and 90% CI from the statistical modeling will be shown by treatment (Section 6.33).
14.2.5.1- 14.2.5.4	Placebo-corrected change-from-baseline QTcF, HR, PR, and QRS ($\Delta\Delta$ QTcF, $\Delta\Delta$ HR, $\Delta\Delta$ PR, and $\Delta\Delta$ QRS) across time point for moxifloxacin analysis	LS mean and 90% CI from the statistical modeling will be shown by treatment (Section 6.33).
14.2.6.1	Scatter plot of QTcF versus RR by treatment	Scatter plots of QTcF and RR intervals by treatment with regression lines will be given (Section 5.4).
14.2.6.2	QTcF-RR decile plot by treatment	QTcF-RR decile plots with linear mixed-effects line and 90% CI will be given (Section 5.4).
14.2.7.1	Mean CBP-307 plasma concentrations over time	Section 6.1 .
14.2.7.2	Mean moxifloxacin plasma concentration over time	Section 6.2 .
14.2.8.1- 14.2.8.3	CBP-307 plasma concentrations and $\Delta\Delta$ QTcF over time	Section 6.1.1 .
14.2.9.1- 14.2.9.3	Hysteresis plot of CBP-307 plasma concentration and $\Delta\Delta$ QTcF connected in temporal order	Section 6.1.1 .
14.2.10.1	Scatter plot of observed CBP-307 plasma concentrations and Δ QTcF with simple linear regression line and LOESS regression	Scatter plot of observed Δ QTcF versus concentration with LOESS line and 90% CI and simple regression line (Section 6.1.2).
14.2.10.2	Scatter plot of observed moxifloxacin plasma concentrations and Δ QTcF with simple linear regression line and LOESS regression	Scatter plot of Δ QTcF versus concentration with LOESS line and 90% CI and simple regression line (Section 6.2).

Number	Title	Comments
14.2.11.1	Scatter plot of observed CBP-307 plasma concentrations and estimated placebo-adjusted $\Delta QTcF$	Scatter plot of placebo-adjusted $\Delta QTcF$ versus concentration with linear mixed-effects regression line and 90% CI of $\Delta\Delta QTcF$ (Section 6.1). Referred to above as “Scatter plot for concentration-QTc model(s).”
14.2.11.2	Scatter plot of observed moxifloxacin plasma concentrations and estimated placebo-adjusted $\Delta QTcF$	Scatter plot of placebo-adjusted $\Delta QTcF$ versus concentration with linear mixed-effects regression line and 90% CI of $\Delta\Delta QTcF$ (Section 6.2). Referred to above as “Scatter plot for concentration-QTc model(s).”
14.2.12.1	Model-predicted $\Delta\Delta QTcF$ (mean and 90% CI) and estimated placebo-adjusted $\Delta QTcF$ (mean and 90% CI) across deciles of CBP-307 plasma concentrations	Section 6.1 . Referred to above as “Decile plots.”
14.2.12.2	Model-predicted $\Delta\Delta QTcF$ (mean and 90% CI) and estimated placebo-adjusted $\Delta QTcF$ (mean and 90% CI) across deciles of moxifloxacin plasma concentrations	Section 6.2 . Referred to above as “Decile plots.”
14.2.13.1	Model-predicted $\Delta\Delta QTcF$ interval at geometric mean peak CBP-307 concentrations	Section 6.1 . Referred to above as “Prediction plots.”
14.2.13.2	Model-predicted $\Delta\Delta QTcF$ interval (mean and 90% CI) at geometric mean peak moxifloxacin concentrations	Section 6.2 . Referred to above as “Prediction plots.”
14.2.14.1	Scatter plot of standardized residuals versus fitted values for CBP-307	Section 6.1.2 .
14.2.14.2	Scatter plot of standardized residuals versus fitted values for moxifloxacin	Section 6.2 .
14.2.15.1	Scatter plot of standardized residuals versus concentrations with LOESS for CBP-307	Section 6.1.2 .

Number	Title	Comments
14.2.15.2	Scatter plot of standardized residuals versus concentrations with LOESS for moxifloxacin	Section 6.2.
14.2.16.1	Scatter plot of standardized residuals versus centered baseline QTcF with LOESS for CBP-307	Section 6.1.2.
14.2.16.2	Scatter plot of standardized residuals versus centered baseline QTcF with LOESS for moxifloxacin	Section 6.2.
14.2.17.1	Box plot of standardized residuals versus nominal time for CBP-307	Section 6.1.2.
14.2.17.2	Box plot of standardized residuals versus nominal time for moxifloxacin	Section 6.2.
14.2.18.1	Box plot of standardized residuals versus treatment for CBP-307	Section 6.1.2.
14.2.18.2	Box plot of standardized residuals versus treatment for moxifloxacin	Section 6.2.
14.2.19.1	Normal Q-Q plot of standardized residuals for CBP-307	Section 6.1.2.
14.2.19.2	Normal Q-Q plot of standardized residuals for moxifloxacin	Section 6.2.
14.2.20.1	Normal Q-Q plots of the estimated random effects for CBP-307	Section 6.1.2.
14.2.20.2	Normal Q-Q plots of the estimated random effects for moxifloxacin	Section 6.2.

8.3 Listings

Number	Title	Comments
16.2.1.1.1- 16.2.1.1.4	QTcF, HR, PR, and QRS intervals - observed and change-from-baseline values for CBP-307 analysis	Section 6.33 for CBP-307 analysis.
16.2.1.2.1- 16.2.1.2.4	QTcF, HR, PR, and QRS intervals - observed and change-from-baseline values for moxifloxacin analysis	Section 6.3 for moxifloxacin analysis.
16.2.2.1	T-wave morphology and U-wave presence for CBP-307 analysis	Section 6.55 for CBP-307 analysis.
16.2.2.2	T-wave morphology and U-wave presence for moxifloxacin analysis	Section 6.5 for moxifloxacin analysis.
16.2.3.1	ΔQTcF and time-matched CBP-307 concentrations for each subject	Data for concentration-QTc analysis (Section 6.1).
16.2.3.2	ΔQTcF and time-matched moxifloxacin concentrations for each subject	Data for assay sensitivity (Section 6.2).

9 Approvals

ERT

[name], PhD

Chief Scientific Officer, Cardiac Safety

DocuSigned by:

[name]

 Signer Name: [name]
Signing Reason: I approve this document
Signing Time: 12-Mar-2022 | 02:57:43 EST

12-Mar-2022 | 02:57:47 EST

Date

[name]

Sr. Principal Biostatistician

DocuSigned by:

[name]

 Signer Name: [name]
Signing Reason: I approve this document
Signing Time: 11-Mar-2022 | 16:02:29 EST

11-Mar-2022 | 16:02:31 EST

Date

Suzhou Connect Biopharmaceuticals, Ltd.

[name]

Project Manager

DocuSigned by:

[name]

 Signer Name: [name]
Signing Reason: I approve this document
Signing Time: 13-Mar-2022 | 19:48:29 PDT

13-Mar-2022 | 19:48:41 PDT

Date

Appendix A: Early Precision QT Analysis

Twelve-lead ECGs will be extracted in up to 10 replicates from each nominal time point pre-specified in the protocol. The median value of each parameter from the set of evaluable beats in each extracted replicate will be calculated, and then the mean of all available medians (minimum 3 medians) from the nominal time point will be used as the subject's reportable value at that time point.

Early Precision QT analysis (formerly High Precision QT analysis) will be performed on all analyzable (non-artifact) beats in the 10 ECG replicates (1 replicate consists of one 14 second ECG). Statistical quality control procedures will be used to review and assess all beats and identify “high” and “low” confidence beats using several criteria including:

- QT or QTc values exceeding or below certain thresholds (biologically unlikely)
- RR values exceeding or below certain thresholds (biologically unlikely)
- Rapid changes in QT, QTc, or RR from beat to beat

Placement of fiducials and measurements of all primary ECG parameters (QT, QTc, RR) in all recorded beats of all replicates will be performed using the iCOMPAS software. All beats that are deemed “high confidence” will not be reviewed by an ERT cardiac safety specialist. All low confidence beats will be reviewed manually by an ERT cardiac safety specialist and adjudicated using pass-fail criteria. The beats found acceptable by manual review will be included in the analysis. The beats confirmed to meet fail criteria will not be included in the analysis.

For the purpose of measuring PR and QRS intervals and to assess T-wave morphology and presence of U-waves, the TQT Plus algorithm will select the 3 ECG replicates with the highest quality score from the ECG extraction window. These 3 ECGs will be analyzed using a semi-automated process to determine these parameters. If 3 consecutive usable beats cannot be identified in at least 2 of the 3 replicates, then all beats in all replicates will be reviewed for that time point using a manual analysis.

If manual analysis is required, then all beats in a minimum of 3 replicates will be reviewed using the iCOMPAS software. The ERT cardiac safety specialist will review all usable beats in Lead II (or an alternate lead) for each replicate and will review and/or adjust the fiducial placements (onset of P, onset of Q, offset of S, and offset of T-wave that were electronically marked) of each waveform and also document the T-wave morphology and the presence of U-waves for each beat. A replicate will only be reported if it has 3 approved, usable beats.

16.1.9.2. Quality Tolerance Limit Definitions

Parameter	Justification for Parameter	Unit Tolerance
Minimum number of evaluable subjects needed.	A shortfall in the overall number of subjects could have had a significant impact on interpretation of the primary endpoint because of limited/insufficient exposure.	N:64

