4. STUDY DESIGN

This will be a Phase I, randomized, double-blind, double-dummy, placebo-controlled, positive-controlled, multi-site, 3-arm study to investigate the effects of therapeutic and supratherapeutic oral doses of CBP-307 on the QTc interval in healthy male and female subjects.

Potential subjects will be asked to read and sign an informed consent form (ICF). After informed consent is obtained, screening procedures and tests to establish subject eligibility to enter the study will be performed within 28 days before Day 1. After informed consent has been obtained but prior to the initiation of study treatment administration, only SAEs will be reported. After placebo administration to all subjects on Day -1, all AEs, whether volunteered, elicited, or noted upon physical examination, will be recorded throughout the study (ie, from Day -1 until the end of the study).

In this study, approximately 68 healthy subjects (at least 30% for each sex) will be randomized into 2 groups (Group 1 and 2) with 34 subjects in each. Group 2 consists of 2 sub-groups (Group 2A and 2B) and each sub-group will be randomized with 17 subjects. Randomized subjects will receive the assigned study drug as a single dose in the morning on Days 1, 2, 3 to 6, 7 to 15, and on Day 16 (placebo will be administered to all subjects on Day -1).

The following treatments will be administered:

- Starting doses of CBP-307 for titration (0.05 mg on Day 1 followed by an up-titrated dose of 0.1 mg on Day 2)
- A therapeutic dose of CBP-307 (0.2 mg, Days 3 to 6)
- A supratherapeutic dose of CBP-307 (0.5 mg, Days 7 to 15)
- Placebo (matched to moxifloxacin and CBP-307)
- Moxifloxacin (400 mg)

Moxifloxacin will be used as a positive control to determine the assay sensitivity of this study with an expected peak QT effect (placebo-corrected change-from-baseline QTcF; $\Delta\Delta QTcF$) of 10 to 15 msec.

[figure not shown]
A summary of dosing timelines per Group is shown below:

Study Treatment Name	Treatment Group	CBP-307	CBP-307 Matched Placebo	Moxifloxacin (Avelox)	Moxifloxacin Matched Placebo
Dosage Formulation		Capsule	Capsule	Tablet	Tablet
Unit Dose Strength(s)/Level(s)		0.05 mg 0.1 mg	Not applicable	400 mg	Not applicable
Dosage Frequency					
Day -1	Group 1 Group 2A Group 2B		1 capsule 1 capsule 1 capsule		
Day 1	Group 1 Group 2A Group 2B	1 × 0.05 mg		1 × 400 mg	1 tablet 1 tablet
Day 2	Group 1 Group 2A Group 2B	1 × 0.1 mg			
Days 3 to 6	Group 1 Group 2A Group 2B	2 × 0.1 mg			

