5. SAMPLE SIZE JUSTIFICATION

Approximately 64 healthy subjects (at least 30% for each sex) will be randomized into 2 groups (Group 1 and 2) with 32 subjects in each. Group 2 consists of 2 sub-groups (Group 2A and 2B) and each sub-group will be randomized with 16 subjects.

Sample Size for Primary Analysis:

A sample size of 28 evaluable subjects per treatment group will provide more than 94.4% power to exclude that CBP-307 causes more than 10-msec QTc effect at clinically relevant plasma levels, as shown by the upper bound of the 2-sided 90% confidence interval (CI) of the model-predicted QT effect ($\Delta\Delta QTcF$) at the observed geometric mean Cmax of CBP-307 in the study. This power is estimated approximately using a 2-sample t-test. The calculation assumes a 1-sided 5% significance level, an underlying effect of CBP-307 of 3 msec and a standard deviation (SD) of the $\Delta QTcF$ of 8 msec for both CBP-307 and placebo treatment groups. Note that this calculation is conservative, since it does not take into account any gain in precision due to the use of all data of each subject with the help of a linear mixed-effects model. The concentration-QTc analysis method is supported by Darpo et al 2015⁴ and Ferber et al, 2015⁵ and consistent with the experiences from 25 recent TQT studies.

Sample Size Considerations for Assay Sensitivity:

To demonstrate assay sensitivity with concentration-QTc analysis, it has to be shown that the $\Delta\Delta QTcF$ of a single dose of 400 mg moxifloxacin exceeds 5 msec (ie, the lower bound of the 2-sided 90% CI of the predicted QTc effect [$\Delta\Delta QTcF$] should exceed 5 msec). In a similarly designed, recent crossover study with 24 healthy subjects (on-file data, ERT), the standard error (SE) for the prediction of the QT effect of moxifloxacin based on the exposure-response

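### The main SAP gives two randomised totals (68 and 64), and the quality tolerance limit of 64 evaluable subjects does not match the power basis of 28 per group (56)

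*SAP*

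**What the plan says.** The file holds two plans, both written to protocol Version 5.0 of 12 January 2022: the main SAP (PK, safety and tolerability) and the cardiodynamic SAP (ECG and concentration-QTc). A one-row quality tolerance table, numbered 16.1.9.2, follows them.

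**Randomised size**

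- Main SAP, Section 4: "approximately 68 healthy subjects (at least 30% for each sex) will be randomized into 2 groups", with 34 per group and 17 in each of Groups 2A and 2B.
- Main SAP, Section 5: "Approximately 64 healthy subjects (at least 30% for each sex) will be randomized into 2 groups", continuing "Group 1 and 2) with 32 subjects in each", and 16 in each sub-group.
- Cardiodynamic SAP, Section 3: 68, 34 per group, 17 per sub-group.
- Cardiodynamic SAP, Section 6.6: 68 again; it "will be randomized into 2 groups (Group 1 and 2) with 34 subjects in each".

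**Evaluable size**

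- Main SAP, Section 5: "A sample size of 28 evaluable subjects per treatment group will provide more than 94.4% power". Section 6.6 of the cardiodynamic SAP makes the same statement. The assay sensitivity calculation in both plans also uses 28 evaluable subjects.
- Table 16.1.9.2: the "Minimum number of evaluable subjects needed" is 64. The justification is that too few subjects overall could affect how the primary endpoint is interpreted.

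Neither plan gives a loss rate that connects 28 evaluable per group to 32 or 34 randomised per group.

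**The concern.** Two current sections of one SAP disagree on the size of the trial, so a reader cannot tell which total the sample size justification supports. The tolerance limit then adds a third statement. It is labelled as the number of evaluable subjects required, yet it exceeds the number on which both plans base their power, and it coincides with a randomised total.

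The limit is tied to interpretation of the primary endpoint. A breach would therefore have to be explained in the study report as a possible weakness of the primary result, even in a trial that had reached the evaluable numbers its own power statement asks for.

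**Working it through.** **Inputs.** Section 5 of the main SAP, repeated in Section 6.6 of the cardiodynamic SAP: margin 10 ms, assumed true effect 3 ms, SD 8 ms in both groups, one-sided 5%, two-sample t-test, 28 evaluable per group. Table 16.1.9.2: limit 64. Randomised totals: 68 or 64.

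**Step 1. Reproduce the plan's power.**

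Distance to the margin = 10 − 3 = 7 ms. SE = 8 × √(1/28 + 1/28) = 2.138 ms. Noncentrality = 7 / 2.138 = 3.27, with df = 54. The noncentral t gives 94.38%, so the stated 94.4% reproduces to rounding.

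For assay sensitivity, a one-sided 5% paired t-test with 28 subjects and effect size 0.64 gives 95.1%. This agrees with the stated minimum of 95%.

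**Step 2. What the power basis needs.** 28 + 28 = 56 evaluable subjects.

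| Evaluable (Group 1 / Group 2 or the reverse) | Total | Power | Limit of 64 |
|---|---|---|---|
| 28 / 28 | 56 | 94.4% | breached |
| 28 / 32 | 60 | 95.5% | breached |
| 31 / 32 | 63 | 96.3% | breached |
| 32 / 32 | 64 | 96.5% | met |
| 34 / 34 | 68 | 97.3% | met |

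So with 56 to 63 evaluable subjects and at least 28 in each group, the limit is breached while power is 94.4% to about 96.3%.

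**Step 3. Losses each number tolerates.**

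- Limit of 64: from 68 randomised, 68 − 64 = 4 losses (4/68 = 5.9%); from 64 randomised, none.
- Power basis of 28 per group: from 34 per group, 6 losses in each group (12/68 = 17.6%); from 32 per group, 4 in each (8/64 = 12.5%). These are maxima and hold only if the losses split evenly.

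**Step 4. Chance of a breach, 68 randomised.** The loss rate is an assumption. Losses are taken as independent, so their number is Binomial(68, d). A breach means 5 or more losses. Both groups keep at least 28 if each of the two Binomial(34, d) loss counts is 6 or less.

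| Assumed loss d | P(fewer than 64 evaluable) | P(at least 28 in both groups) |
|---|---|---|
| 5% | 25% | 99.7% |
| 10% | 82% | 91% |

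If 64 are randomised, as in Section 5 of the main SAP, the limit holds only with no loss at all: 0.95^64 = 3.8% at an assumed 5% loss.

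**The case against.** A limit set above the power requirement is not wrong in itself. It gives an earlier warning. Both 64 and 68 exceed the 56 evaluable subjects needed, and the power statement reproduces. The QTc conclusion in Section 6.1 and the assay sensitivity criterion in Section 6.2 of the cardiodynamic SAP do not use the limit. The table's numbering also fits neither plan, so it may be a separate appendix bound into the file. All of this stands, and it keeps the severity low. It does not explain why 64 is labelled as the evaluable number required when both plans say 28 per group, and it does not touch the 68 against 64 contradiction.

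A reader might go further in four ways that the documents do not support.

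- *A single total of 64 could hide one group falling below 28.* It could not. With 34 per group, 64 evaluable leaves at least 64 − 34 = 30 in each group; with 32 per group it leaves 32 in each. The other group would need at least 64 − 27 = 37, more than either section randomises.
- *A breach means the trial has failed.* The table attaches no action, stopping or failure rule. It says only that a shortfall could affect interpretation.
- *The plan implies a 12.5% loss, because 28 is 12.5% below 32, so a breach is almost certain.* No section derives 28 from 32 by a loss allowance. Applying that rate to 68 randomised would also mix the two versions of the trial size.
- *68 is established as the correct total.* Three of the four statements say 68, which makes it the likelier figure, but the protocol is not shown.

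**Conclusion.** The point holds as an internal inconsistency in two places. The main SAP states both 68 and 64 randomised. The tolerance limit calls 64 the required number of evaluable subjects, although the power basis in both plans is 56, as 28 per group. That 64 was carried over from the randomised total in Section 5 is an inference from the matching figure.

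The practical effect is conditional. It arises only with 56 to 63 evaluable subjects and at least 28 in each group. How likely that is depends on a loss rate the documents do not give: with 68 randomised, the chance of falling below 64 is about 25% at an assumed 5% loss and 82% at 10%. The estimates, confidence intervals, populations and decision rules are unaffected. Severity is minor to moderate: a correction to figures the trial relies on for reporting and quality oversight.

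**What to change.** 1. Check Section 5 of the main SAP against the protocol and use one randomised total throughout. On the text available, 68 (34 per group, 17 per sub-group) appears to be the current figure.
2. In Table 16.1.9.2, choose one of the following:
   - state the limit as at least 28 evaluable in Group 1 and at least 28 in Group 2;
   - relabel 64 as a randomised number;
   - keep 64 evaluable as a deliberately stricter early-warning level, say so, and give the assumed loss rate.
3. If the limit is lowered, state it per group and not as a bare total of 56. A total of 56 would admit 34 + 22, where power falls to 93.5%, below the stated 94.4%.
4. Add one sentence to the sample size sections giving the loss allowance that connects 28 evaluable to the number randomised per group.

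The cost is text edits and a check against the protocol. No model, analysis population or decision rule changes.
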